4.1 General Principles

The statistical evaluation will be performed by using the software package SAS release 9.4 or higher (SAS Institute Inc., Cary, NC, USA).

All variables will be analyzed by descriptive statistical methods. The number of data available, mean, standard deviation, minimum, median, and maximum will be calculated for metric data. Frequency tables will be generated for categorical data.

The analysis will be based on the Clinical Pharmacology Standard (CLIPS), version 3.0 [2].

Tables and listings describing the impact of COVID-19 on the study will be created as appropriate. If needed, the onset of the COVID-19 pandemic will be considered as 11 MAR 2020 (date when the WHO declared the COVID-19 pandemic).

VitalPatch and AVIVO data will not be transferred to the clinical database and will be considered in the scope of the biomarker analyses.

All planned statistical analyses will be explorative. A confirmatory statistical analysis is not intended. Thus, no adjustment for the type I error level will be done.

4.2 Handling of Dropouts

A subject who discontinues study participation prematurely for any reason is defined as a “dropout” if the subject has already been started one device monitoring period.

As far as possible patients who are considered as dropouts will be replaced until a number of at least 60 evaluable datasets for HFpEF patients and 20 for HFrEF patients has been reached.

4.3 Handling of Missing Data

Missing data will not be replaced. Analyses will be performed considering all data observed for the respective analysis sets.

All missing or partial data will be presented in the subject data listing as they are recorded on the Case Report Form.

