### **3. Introduction - amended**

#### **Rationale and Background**

Heart failure (HF) is known to be a major public health problem and a major cause of mortality and morbidity. It has a prevalence of up to 22% in elderly, and aging of population worldwide will result in a further rise in the HF prevalence by 50% over the next 10-15 years [1, 2].

Acute decompensated heart failure is constantly increasing in prevalence and is strongly associated with mortality and morbidity, including frequent hospitalizations [3, 4]. The high percentage (30 – 60%) of readmissions within 6 months is particularly noteworthy [5].

Heart failure with preserved ejection fraction (HFpEF) currently accounts for more than 50% of all HF cases and shows rising incidence [6], and outcomes among these patients are as poor as those with HF and reduced ejection fraction (HFrEF). Previous HF trials have focused primarily on reduction of CV mortality and/or readmission risk, whereas studies among hospitalized patients have largely focused on acute symptoms. Given the fact that patients with HFpEF are much older and have significant comorbidity burden compared to their peers with HFrEF, it is difficult to conceive that one drug or device can reduce mortality or hospitalization risk in these patients.[7] Though intensively managed, these patients remain symptomatic and have substantially reduced functional capacity and quality of life (QoL).

Improvement in mortality remains the gold standard outcome for HF clinical trials, and indeed many therapies in patients with HFrEF were able to reduce the risk of death. However, in HFpEF patients, the competing risk for death by complex comorbidities is substantial among these patients. Effectively targeting mechanisms related to HFpEF may improve underlying pathophysiology and subsequently patient status; however, this may be insufficient to alter overall mortality among HFpEF patients. Thus, in an older HFpEF population due to the competing risk for death, it may be prohibitively difficult to improve mortality as a singular goal of therapy. Reducing the risk of hospitalizations is an important consideration as they are associated with poor outcomes, high costs and impaired QoL. However, one of the major issues is that it may reflect regional practices [8].

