6.5 Other evaluations

If not stated otherwise, analyses will be performed on the FAS population.

For each parameter (6-minute walking distance, KCCQ, PRO), subjects will be split into classes representing clinically relevant worsening versus no relevant change or improvement. The exact definition will be given in the respective subsection.

6.5.1 6-minute walking distance

The 6MWD will be summarized by visit and cohort/total using descriptive statistics including arithmetic mean, SD, median, minimum, and maximum.

A frequency table will be created for the comparison of the subjects with and without observed worsening according to the following definitions:

- Worsening: decrease in 6MWD by at least 30 meters
- No worsening: decrease in 6MWD by up to 30 meters, no change or increased 6MWD

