6.5.2 Quality of life / PRO

6.5.2.1 KCCQ

The summary scores “Total Symptom Score”, “Clinical Summary Score”, and “Overall Summary Score” as well as the “Physical Limitation Scores” will be summarized using frequency counts by cohort and total.

A frequency table will be created for the comparison of the subjects with and without observed worsening according to the following definitions:

- Worsening: decrease in KCCQ score by at least 5 points
- No worsening: decrease in KCCQ score by up to 5 points, no change or increased KCCQ score

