6.5.2.2 PRO

The “Overall Activity Score” will be calculated as the sum of the following mean items: walking general, housework, and exercise.

The parameters

- Overall Activity Score
 - o General physical activity item (1 unit change on weekly average score)
 - o Physical activity impression of change item (2 unit change)
 - o Fatigue impression of change item (2 unit change)
 - o Shortness of breath impression of change item (2 unit change)
 - o Swelling impression of change item (2 unit change)

will be summarized using frequency count.

In addition, response with respect to the anchor measures derived from the following individual items

- General physical activity item (1 unit change)

- Physical activity impression of change item (2 unit change)
- Fatigue impression of change item (2 unit change)
- Shortness of breath impression of change item (2 unit change)
- Swelling impression of change item (2 unit change)

will be tabulated using frequency tables.

A frequency table will be created for the comparison of the subjects with and without observed worsening according to the following definitions:

- Worsening: decrease in “Overall Activity Score” by at least 2 units
- No worsening: decrease in “Overall Activity Score” by up to 2 points, no change or increased “Overall Activity Score”

The univariate linear mixed model (LMM) for the repeated values of the “Overall Activity Score” is

$$Y_{ij} = \mu + S_i + v_j + \beta base_i + E_{ij}$$

where μ is a constant common to all observations, S_i is the normally distributed random variable with mean zero and variance σ_d^2 corresponding to subject i , v_j is the fixed effect corresponding to visit j , and E_{ij} is a normally distributed random variable with mean zero and variance σ_e^2 , independent of S_i . The variable “base” is the baseline measurement included as covariate and β is the corresponding regression parameter.

Based on the described LMM, point estimates and 90% confidence intervals for the “Overall Activity Score” will be calculated.

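### A patient with no second six-minute walk because of death or heart-failure-related inability falls in neither worsening class and leaves the DynaPort subgroups built on it

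*SAP*

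**What the plan says.** SAP 6.5 states that for 6MWD, KCCQ and PRO "subjects will be split into classes representing clinically relevant worsening versus no relevant change or improvement". Each class is then defined by a measured change:

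- **6MWD (SAP 6.5.1):** "Worsening: decrease in 6MWD by at least 30 meters", against "No worsening: decrease in 6MWD by up to 30 meters, no change or increased 6MWD".
- **KCCQ (SAP 6.5.2.1):** "Worsening: decrease in KCCQ score by at least 5 points". No follow-up visit is named.
- **PRO (SAP 6.5.2.2):** "Worsening: decrease in “Overall Activity Score” by at least 2 units". No follow-up visit is named.

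There is no third class for death, inability to be tested or missing data. The general rule in SAP 4.3 is "Missing data will not be replaced"; the analyses use whatever was observed in the analysis set concerned.

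SAP 6.5.4.1 analyses the DynaPort data in subgroups formed by these classes. SAP 5.1 admits a patient to the device set on the strength of one wearing period. Under SAP 6.4.1, deaths and adverse events leading to discontinuation appear in listings only.

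**The concern.** The class is labelled as clinically relevant worsening, yet the definition can only be met by someone who has a second test. Death, or heart failure severe enough to prevent walking, is deterioration by any ordinary reading. A patient lost in that way is counted neither as worsened nor as not worsened.

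Two outputs are affected. The 6MWD worsening table describes only patients tested twice. The DynaPort subgroups by 6MWD class inherit the same restriction, so valid early activity data are set aside because a later walk is missing. The SAP still lists the objective of relating physical activity to adverse events and clinical outcomes. The worsening subgroups are its only planned comparison of DynaPort data with clinical deterioration. Recruitment stopped early (SAP 2), so each patient who drops out of the classification carries more weight.

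**Working it through.** **Inputs**

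- 6MWD is scheduled at Visit 1 (Day 0) and Visit 4 (Day 84 ± 2): Protocol Table 9–1; SAP 3 agrees.
- DynaPort is worn on Days 9–16 and Days 77–84: Protocol Table 9–1, footnote 2.
- KCCQ is due at Visit 1, Day 16 and Visit 4 (Protocol Table 9–1). KCCQ and PRO are completed on a tablet handed to the patient for the study (Protocol 9.7.2).
- Target size is 60 HFpEF + 20 HFrEF = 80 completers, with no power calculation (Protocol 10.4). The number actually recruited is lower and not given (SAP 2).
- No worsening, death or dropout rate is stated, so there is no figure of the plan's own to reproduce here.

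**Step 1: trace one patient.** Take a hypothetical patient who wears the DynaPort on Days 9–16 and dies on Day 40. One wearing period puts the patient in the device set. There is no second 6MWD, so no change can be computed, neither 6MWD definition is met, and nothing is imputed. The patient is absent from the 6MWD table and from the DynaPort display by 6MWD class.

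**Step 2: effect on the share worsened.** Let d be the share unclassified, w the worsening share among classified patients and q the share among unclassified patients.

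- Share in all patients = w(1 − d) + qd = w + d(q − w)
- Understatement = d(q − w)

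All rates below are assumed. With d = 10%:

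| q | w = 15% | w = 30% |
|---|---|---|
| 0 | 13.5% | 27.0% |
| 0.15 | 15.0% | 28.5% |
| 0.30 | 16.5% | 30.0% |
| 0.50 | 18.5% | 32.0% |
| 1 (all counted as worsened) | 23.5% | 37.0% |

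For example, with q = 1 and w = 15%: 0.15 + 0.10 × (1 − 0.15) = 0.235. With q = 1 and w = 15%, d = 5% gives 0.15 + 0.05 × 0.85 = 19.25%, and d = 20% gives 0.15 + 0.20 × 0.85 = 32.0%.

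In whole patients, with 80 enrolled and 8 unclassified: observed 11/72 = 15.3%; with all 8 counted as worsened, 19/80 = 23.8%; with none of them worsened, 11/80 = 13.8%.

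The shift is zero when q = w and changes sign when q < w.

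**Step 3: KCCQ and PRO.** If the Day 16 KCCQ can serve as the follow-up value, a patient stable at Day 16 who later dies is classed as not worsened. If Visit 4 is required, the same patient is unclassified. The SAP does not choose. For PRO, the second period starts at Visit 3 and Protocol Appendix 16.1 accepts a weekly average from four or more days. A patient lost shortly before Visit 4 can therefore still have a second-period value; one lost before Visit 3 cannot.

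**Step 4: the activity contrast.** Its bias depends on how active the unclassified patients were compared with those observed to worsen, which the documents do not indicate. Patients lost before Visit 3 have no second DynaPort period, so classifying them cannot alter a contrast in change between periods. It can alter only the first-period display.

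**The case against.** Four stronger readings are tempting, and the documents do not support them.

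- **That all three classifications are restricted to survivors who attend Visit 4.** This fits 6MWD only. KCCQ has a Day 16 value, KCCQ and PRO are collected on a patient-held tablet, and no follow-up visit is named for either.
- **That worsening is understated as a matter of fact.** This needs q > w. Setting q = 1 is a convention that neither document adopts, and Step 2 shows the shift can be zero or negative.
- **That the cited readmission rate shows how many will be lost.** The 30–60% in Protocol 3, described with the words "of readmissions within 6 months is particularly noteworthy", concerns readmission in acute decompensated heart failure over 6 months. Visit 4 is at 12 weeks, a readmitted patient may still be tested, and stable ambulatory patients are now eligible. The figure is not a missingness rate.
- **That the activity contrast is biased toward no difference.** No direction can be derived (Step 4).

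The protocol also softens the loss. It asks for a final assessment at withdrawal where possible (6.4.1), foresees a 6MWD at premature discontinuation and allows rests during the walk (9.7.3). A severely limited walker can therefore still record a short distance and be classed as worsened. In addition, disposition is tabulated and deaths are listed, so a reader could trace the missing patients in a small study.

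These points limit the size and the severity. They do not cover the patient who dies or cannot walk at all, and the SAP does not say whether a discontinuation value enters the classification.

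**Conclusion.** The gap is real for 6MWD. Patients with no second walk because of death or heart failure are in neither class and leave both the 6MWD table and the DynaPort subgroups by 6MWD class, whatever early activity data they have. The share worsened is then understated by d(q − w), provided these patients count as worsened or worsen more often than those tested. The actual size cannot be computed from the documents. The range of 15% to 23.5% rests on an assumed 10% unclassified, an assumed 15% observed worsening and q between 0.15 and 1.

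For KCCQ and PRO the fault is an unnamed follow-up value, with a smaller loss and, for KCCQ, the possibility that a patient who later dies is classed as not worsened. The direction of any bias in the activity contrast is unknown. Because all analyses are exploratory (SAP 4.1), no error rate or confirmatory conclusion is touched. Severity is minor, and the case for changing the plan is that the improvement is cheap.

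**What to change.** Keep the observed-case tables as planned and make these additions to the SAP:

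1. For each of 6MWD, KCCQ and PRO, name the follow-up value that defines worsening, and state whether a premature-discontinuation value counts.
2. Add a row to each worsening table for patients who died or were not assessable because of heart failure, separate from other missing data. Use the adverse event outcome (which includes fatal) and the primary reason for discontinuation, both already recorded.
3. Add one sensitivity table that counts these patients as worsened, and show first-period DynaPort data by that class.

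The cost is one row per table, one sensitivity table with its DynaPort display, and a few sentences of definition. No new patient procedure is needed. There are two drawbacks. The sensitivity class mixes event-based with test-based worsening, so it should be labelled as such. The protocol also describes no reason field for a walk not done at an attended visit, so some reasons may not be recorded; those patients would stay under other missing data.

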4.4 Interim Analyses and Data Monitoring

No interim analyses are planned. The final analysis will be performed after end of the study which is the date the analytical dataset is completely available.

4.5 Data Rules

4.5.1 Baseline

Baseline is defined as the first visit after the screening visit.

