**Table 9–1: Tabulated overview on study procedures and variables collected during the study - amended**

Study period	Screening phase		Observational phase				Safety FU call
	Scr 	1	2		3	4	
Visit number	site	site	site		site	site	☎
	Screen assess	At discharge / ambulatory visit					
Week after discharge / Visit 1			2	3	11	12	
Day and allowed deviations	-9 → -1	0	9±2	16±2	77±2	84±2	6 months ±4 weeks
Signed informed consent form	•						
Inclusion / exclusion criteria	•						
KCCQ		•		•		•	
Daily and weekly PRO*			→----1 st ----←		→----2 nd ----←		
Demographic data	•						
Medical and surgical history	•						
Height	•						
Weight	•	•	•			•	
12-lead ECG	•	•				•	
NYHA class	•	•	•			•	
Blood pressure and heart rate	•	•	•		•	•	
Adverse Events incl. healthcare resources	•	•	•		•	•	•
Concomitant medication	•	•	•		•	•	•
Echocardiography		• 					
Six-minute walking distance		•				•	
DynaPort (for 7 days)  →start ←end			→----1 st ----←		→----2 nd ----←		
VitalPatch  (for 5 days)  →start ←end		→--1 st --←	→ 2 nd and 3 rd ←		→ 4 th and 5 th ←		
Blood sample for biomarkers 	• 	•				•	

 during hospitalization; alternatively, in ambulatory patients

 DynaPort monitoring periods: For one week, after Visit 2 (Days 9-16) and from Visit 3 to Visit 4 (Days 77-84)

VitalPatch monitoring periods: first 5 days after hospital discharge / Visit 1 (Day 0-5), one week after Visit 2 (Day 9-16) and from Visit 3 to Visit 4 (Days 77-84)

 central lab assessments: NTproBNP, hs-copeptin, hs-TNT, optionally: GDF15, IGFBP7, sST2, Gal3

\* Concurrently evaluating PRO will be completed daily and weekly during DynaPort and VitalPatch parallel monitoring period

 only applicable to hospitalized patients

 within ± 72 h of Visit 1 / discharge day

 Adaption of timing and number of study related measurements to simplify procedures as per Amendment 3 (Section 15.3)

 Replacement of AVIVO MPM with VitalPatch Biosensor as per Amendment 2 (Section 15.2)

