- Explore the relationship between PA, 6-minute walking distance (6MWD), PRO, biomarkers, adverse events/clinical outcomes
- Investigate the accuracy of patients' self-reports (PRO, e.g. KCCQ) of time spent on PA in real life vs. objective assessment by the DynaPort Move Monitor and VitalPatch biosensor³

¹ Will not be addressed due to change from AVIVO to VitalPatch (ECG data only)

² Will not be addressed due to change in procedure schedule

³ Meaningful assessment not possible given the provided variables.

Given the data situation (not all parameters provided by the vendor) and the low number of subjects (recruiting stopped early due to recruiting issues), not all the original objectives mentioned above will be addressed.

3. Study Design

This is a non-randomized, multi-center, observatory prospective patient study. The study will be conducted in several centers in EU and non-EU.

[figure not shown]
Patients hospitalized due to heart failure as well as ambulatory patients with heart failure will be included in this study. Overall approx. 80 subjects have to complete at least all device monitoring periods:

- Approx. 60 subjects with established diagnosis of heart failure with preserved ejection fraction (HFpEF; EF ≥ 45%) (Cohort 1) and
- Approx. 20 subjects with established diagnosis of heart failure with reduced ejection fraction (HFrEF; EF ≤ 35%) (Cohort 2).

All patients will receive the AVIVO / VitalPatch biosensor at 5 monitoring periods (5 patches each subject in total, monitoring period 7 / 5 days each period) and the DynaPort Move Monitor (belt) at 2 monitoring periods (7 day monitoring each period). Results from both devices are not visible to investigator and subjects to avoid bias on treatment decisions.

Biomarkers will be investigated during the hospital stay (only in case patient is hospitalized), at visit 1, and at visit 4. A 6-minute walking test will be performed at visit 1 / discharge and after 11-12 weeks.

Design overview

Abbreviations: KCCQ = Kansas City Cardiomyopathy Questionnaire score; QS = Questionnaire for patient reported outcomes (daily and weekly); 6MWD = 6 minute walking distance; FUP = follow up visit

4. General Statistical Considerations

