5.1 Assignment of analysis sets

In absence of intervention and randomization the statistical analysis sets are defined as follows:

Full analysis set (FAS) [= Safety analysis set (SAF)]

All subjects that were enrolled into the study and that wore at least one device will be included in the FAS.

Device Set (DES)

All subjects with DynaPort parameters for least one wearing period will be included in the DES.

6. Statistical Methodology

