6.5.4 Wearable data

6.5.4.1 DynaPort

The analysis of the DynaPort data will be performed on on the DES population.

Summary statistics for the wearing time of DynaPort data will be presented by cohort and wearing period.

The following parameters (mean, minimum and maximum over wearing period) will be analyzed:

- Steps
- Physical Activity Level (PAL)
- Total Energy Expenditure (TEE)

- Active time (Sum of standing, shuffling, walking, stair walking and cycling time)
- Time spent in different activity states (sedentary / light / moderate / vigorous)

The DynaPort parameters mentioned above will be summarized by cohort/total and visit using descriptive statistics including arithmetic mean, SD, median, minimum and maximum.

Statistics will be presented for the original data and difference to baseline.

Graphical displays of individual data as well as mean values with standard deviations will be created for each parameter by cohort using planned sampling times.

The univariate LMM for the repeated values of the DynaPort parameters is

$$Y_{ij} = \mu + S_i + v_j + \beta base_i + E_{ij}$$

where μ is a constant common to all observations, S_i is the normally distributed random variable with mean zero and variance σ_d^2 corresponding to subject i , v_j is the fixed effect corresponding to visit j , and E_{ij} is a normally distributed random variable with mean zero and variance σ_e^2 , independent of S_i . The variable “base” is the baseline measurement included as covariate and β is the corresponding regression parameter.

Based on the described LMM, point estimates and 90% confidence intervals for the DynaPort parameters will be calculated.

Subgroup analyses will be performed for the defined categories (worsening / no worsening) of 6MWD, KCCQ and PRO.

7. Document history and changes in the planned statistical analysis

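### The SAP's single baseline is Visit 1, but DynaPort and the diary start at Visit 2, so the DynaPort change from baseline and both mixed models cannot be run as written

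*SAP*

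**What the plan says.** SAP 4.5.1 states "Baseline is defined as the first visit after the screening visit" and gives no exception by parameter. Protocol 9.2 shows that this is Visit 1 (Day 0), and Protocol 5, under the secondary variables, also names Visit 1 as baseline for primary and secondary variables alike.

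Protocol Table 9-1, footnote 2, sets the belt schedule: "DynaPort monitoring periods: For one week, after Visit 2 (Days 9-16) and from Visit 3 to Visit 4 (Days 77-84"). The Synopsis (Methodology) and Table 9-1 run the daily and weekly diary alongside those two belt periods. The Visit 1 procedure list in Protocol 9.2 has neither the belt nor the diary.

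For DynaPort, SAP 6.5.4.1 plans that "Statistics will be presented for the original data and difference to baseline". It then fits a linear mixed model with a random subject effect, a fixed visit effect and a baseline covariate, from which "point estimates and 90% confidence intervals for the DynaPort parameters will be calculated". SAP 6.5.2.2 uses the same model for the diary-based Overall Activity Score; there too the variable base "is the baseline measurement included as covariate". SAP 3 confirms that each subject wears "the DynaPort Move Monitor (belt) at 2 monitoring periods (7 day monitoring each period"). SAP 5.1 admits subjects to the device set on one period alone: "All subjects with DynaPort parameters for least one wearing period will be included in the DES".

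**The concern.** The baseline rule points to a visit at which neither instrument is in use. Two planned items therefore have no value for any subject: the DynaPort difference to baseline, and the covariate in both mixed models. SAP 4.3 rules out replacing missing data, so nothing fills the gap.

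DynaPort carries the primary variable in this SAP. SAP 4.1 says "VitalPatch and AVIVO data will not be transferred to the clinical database", so the belt is the only wearable analysed here. The Synopsis time frame for the primary variable covers baseline level, change over time and within-subject spread. The change summaries and the only model planned for the belt data would depend on a baseline and a model form chosen by the programmer. The SAP text gives no rule for either.

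The diary worsening class in SAP 6.5.2.2 (a fall of at least 2 units in the Overall Activity Score) can be formed from period 1 to period 2, but its reference period is not named. The DynaPort subgroups defined by that class inherit the same gap.

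**Working it through.** **Step 1. Baseline rule against schedule** (Protocol Table 9-1 and 9.2).

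| Parameter | At Visit 1 (Day 0) | At Visit 2 (Day 9 ± 2) |
|---|---|---|
| 6MWD, KCCQ, 12-lead ECG, biomarkers | yes | no |
| DynaPort | no | starts; period 1 is Days 9–16 |
| Daily/weekly diary | no | starts, alongside DynaPort |

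The earliest DynaPort or diary value comes 9 − 2 = 7 to 9 + 2 = 11 days after Visit 1, so no visit window bridges the gap. Table 9-1 places Visit 1 under the screening phase, so one could ask whether Visit 2 was meant. In that case 6MWD, KCCQ, ECG and biomarkers would lose their baseline. No single visit serves every parameter.

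**Step 2. What is missing as written.** SAP 6.5.4.1 lists steps, PAL, TEE, active time and four activity states, which makes 8 parameters. Each is taken as mean, minimum and maximum, so 8 × 3 = 24 change summaries are planned and 0 can be computed. Neither of the two mixed-model specifications has a covariate value.

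**Step 3. Period 1 as baseline, period 2 as the only outcome.** Each subject has one record. The fixed part has three columns (constant, visit, base) but rank 2, because visit takes one value and is aliased with the constant. Only the sum of subject and residual variance enters the likelihood, so the two cannot be separated.

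**Step 4. Period 1 as baseline, both periods as outcomes.** Take unit variances and between-period correlation ρ.

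- Regressing the subject mean on period 1 leaves residual variance (1 − ρ²)/4, so the between-subject mean square is (1 − ρ²)/2. The within-subject mean square is 1 − ρ.
- Implied subject variance = half the difference = −(1 − ρ)²/4 = −0.0625, −0.0225, −0.0025 at ρ = 0.5, 0.7, 0.9. It is negative throughout, so REML is pushed to zero.
- With subject variance zero, the pooled residual variance is (1 − ρ)(3 + ρ)/4.
- Period 2 minus period 1: SE relative to the paired SE = √((3 + ρ)/4) = 0.935, 0.962, 0.987.
- Period-2 mean: SE relative to a regression of period 2 on period 1 (residual variance 1 − ρ²) = √((3 + ρ)/(4(1 + ρ))) = 0.764, 0.738, 0.716. The point estimate is the same.

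**Step 5. Simulation** of the Step 4 model: 20,000 samples per cell, closed-form balanced REML. Entries are for ρ = 0.5 / 0.7 / 0.9.

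| n | Subject variance = 0 (%) | SE ratio, contrast | Coverage of 90% contrast interval (%) | SE ratio, period-2 mean |
|---|---|---|---|---|
| 20 | 91.3 / 78.4 / 53.2 | 0.940 / 0.964 / 0.984 | 88.0 / 89.0 / 89.4 | 0.771 / 0.742 / 0.719 |
| 40 | 99.1 / 94.0 / 67.9 | 0.938 / 0.963 / 0.987 | 87.8 / 88.6 / 90.0 | 0.767 / 0.740 / 0.717 |
| 80 | 100 / 99.5 / 84.9 | 0.937 / 0.963 / 0.987 | 87.6 / 88.9 / 89.7 | 0.765 / 0.738 / 0.717 |

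A general iterative mixed-model fit at n = 40, ρ = 0.7 (60 samples) gave a contrast SE ratio of 0.960 and a subject variance below 0.0001 in 49 of 60. The correlations and n are assumptions. The SAP gives no achieved number and says only that it is low; 80 is the planned total.

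**The case against.** With two belt periods, the only workable difference is period 2 minus period 1, and most programmers would take it. The count of 24 shows how often one missing sentence recurs, not how much information is lost. The analysis is declared explorative, and the affected SAP sections ask only for point estimates and intervals, not variance components. With one record per subject, failure to separate the variances does not bias the period-2 estimate, and the visit column is redundant rather than wrong. With both periods as outcomes, the contrast interval is nearly right. SAP 4.1 also relies on a company standard that is not available here, and SAP 4.6 allows documented changes after data review.

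Much of this stands as a limit on the damage. It does not remove the defect, because an easily guessed baseline still leaves a model that two periods cannot support. SAP 2 also keeps between- and within-subject variability as an objective with no footnote dropping it, although it says in general that not all objectives will be addressed. Protocol 5 wants standard deviations for later sample sizes. A model that usually returns zero subject variance cannot supply the between-subject part.

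Two further points stand. The 0.72–0.77 ratio depends on its comparator: against the unconditional period-2 mean of a model without the covariate, the ratio is √((1 − ρ)(3 + ρ)/4) = 0.66, 0.53, 0.31. And 6MWD moved to Visit 1 only with Amendment 3, so any subject enrolled earlier may lack a Visit 1 value for it.

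**Conclusion.** The concern holds. Under SAP 4.5.1 the DynaPort difference to baseline and the covariate of both mixed models have no value for any subject, and no other single visit repairs the rule. This follows from the documents alone.

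Once period 1 is taken as baseline, the size of the model problem depends on what the 90% interval is for, which the SAP does not say. For the period contrast the effect is small (SE 0.94–0.99 of proper, coverage about 88–90%). For the period-2 mean the SE is about a quarter too small against a regression on period 1. Subject variance is estimated as zero in 53–91% of samples at n = 20, 68–99% at n = 40 and 85–100% at n = 80. These figures rest on assumed correlations of 0.5–0.9.

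Original-data summaries by visit, wearing-time summaries and plots of original values are unaffected and still serve the primary objective. KCCQ has its Visit 1 value. This should be fixed, but it does not undermine the study.

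**What to change.** - **SAP 4.5.1:** define the DynaPort and diary baseline as period 1, the period started at Visit 2, and keep Visit 1 for parameters collected there. Write period 1 and not first available period: the device set accepts subjects with one period, and a subject with period 2 only would otherwise receive period 2 as baseline. State that a subject without period 1 data has no difference to baseline. Say what applies to 6MWD in any subject enrolled before Amendment 3.
- **SAP 6.5.2.2 and 6.5.4.1:** choose one model. Form (a) has both periods as outcomes and a random subject effect, without a baseline covariate, as in the base model of Protocol 10.3.3.1. Form (b) is a regression of period 2 on period 1 without the random effect. Form (a) keeps subjects with one period and gives the between- and within-subject variances. The two forms give different intervals for the period-2 mean, so they are not interchangeable.
- **Same sections:** state whether the 90% interval is for the period contrast or the period means.
- **SAP 6.5.2.2:** name period 1 as the reference for the diary worsening class.

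The cost is wording in three SAP sections and one changed model statement, with no new data.
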